7.2. Randomization and Statistical Methods

7.2.a. Randomization. Participants in the Cognitively Normal, the MCI, and Parkinson groups will be independently assigned to Sham and Treatment groups on a 1:1 ratio. For the Cognitively Normal group, we anticipate an N of 35 in each treatment group. For each MCI group, we anticipate an N of 10 per treatment group. For the PD group, we anticipate an N of 20 per treatment group. Randomization will be stratified according to age and MoCA/MMSE scores so as to prevent different average ages or cognitive status scores between the treatment groups. Treatment assignment will be pseudorandomized in order to have comparable distributions of age and cognitive screening scores across Sham and Treatment interventions. Procedures will be followed so that group assignments are not available to individuals administering and scoring baseline/pre-intervention and post-intervention cognitive/mood data.

7.2.b. Missingness and Intent to Treat.

All data will be checked for missingness, out-of-range values, and distributional form (i.e., normality, homogeneity of variance). Decisions regarding use of parametric vs. nonparametric statistics will be based on the results of those analyses. Standard summary statistics will be provided for pre- and post-stimulation. Intent to treat analysis will be used to reduce selective attrition bias; participants who are unwilling/unable to continue with intervention will be encouraged to attend the post intervention testing, if possible. Thus, statistical analyses will be performed on two data sets: 1) on all subjects who were successfully screened, randomized and able to participate in at least 1 week of the assigned intervention, regardless of study

completion (intention-to-treat analysis); and 2) on subjects who were successfully screened, randomized and able to complete at least 80% of the treatment assignment.

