Revitalize Cognition: Near Infrared Stimulation in Older Adults

NCT06688357

11/13/2024

Updated Statistical Plan

Updated Statistical Analysis Plan

Due to the small N, we examined cognitive and emotion outcome variables using change scores (post intervention – baseline). These change scores were evaluated as a function of treatment group (active, sham) using independent t-tests. Cohen's D effect sizes were computed to guide selection of potential cognitive measures for use in future clinical trials, as appropriate.

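### The main treatment comparisons omit age and cognitive screening score, the factors used to balance allocation; to the extent that these predict change, the tests are conservative and lose precision

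*Protocol*

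**What the plan says.** **Allocation (Protocol 7.2.a).** Each diagnostic group is "independently assigned to Sham and Treatment groups on a 1:1 ratio". The balancing factors are explicit: "Randomization will be stratified according to age and MoCA/MMSE scores". The stated aim is that the arms should not differ on average in either factor. The mechanism is described this way: "Treatment assignment will be pseudorandomized in order to have comparable distributions of age and cognitive screening scores across Sham and Treatment interventions". Cut-points, block size and algorithm are not given.

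**Group sizes (Protocol 7.2.a).** The planned sizes per arm are 35 (cognitively normal), 10 (each of the two MCI groups) and 20 (Parkinson disease).

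**Main tests.** Protocol 7.3 analyses the diagnostic groups separately, with a mixed ANOVA whose only factors are group (active, sham) and occasion (before, after). The SAP forms post-minus-baseline change scores and says: "These change scores were evaluated as a function of treatment group (active, sham) using independent t-tests". It names no covariate.

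**Where the factors do appear.** Section 7.3 plans additional analyses with age as a predictor of change and as a possible moderator or mediator. The cognitive screening score is in none of them. The only variable named outright as a covariate is the skin-type questionnaire (6.6.5c), which is not a balancing factor.

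**The concern.** Balancing on a factor makes the arms alike on it, so that factor contributes little to the chance difference between arms. A test that omits the factor still counts its variation as error. Its standard error then describes simple randomisation, which was not the method used. If age or screening score predicts the outcome being tested, the reported standard error is too large, p-values are too high, and the precision bought by the balanced design goes unreported.

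At stake is efficiency in a small pilot. The SAP itself cites the small sample, and its purpose is to pick measures for later trials. This point concerns the factors used to allocate, which is a separate matter from adjusting for each outcome's own baseline score.

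**Working it through.** The documents give no power, effect size, SD or type I error for these tests, so there is no planned figure to reproduce.

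**Inputs from the documents.** Balancing factors: age and MoCA/MMSE (7.2.a). Sizes per arm: 35, 20 and 10 (7.2.a). Tests: group by occasion ANOVA (7.3) and t-test on change (SAP). With two occasions, the group-by-occasion test is the same as the t-test on change, so one calculation covers both.

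**Assumptions.** Two-sided 5% level: none is stated for the cognitive, mood or motor tests, and the only .05 threshold is for the fMRI measure in 6.8. R2, the share of change-score variance explained by age and screening score together, is not given and is varied from 0 to 0.30. The simulation uses blocks of 4 within four strata (median splits of both factors).

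**Step 1, large-sample formula.** With close balance, the standard error is overstated by 1/√(1−R2), and the true size of the test is 2 × [1 − Φ(1.96/√(1−R2))]. For example, at R2 = 0.10, 1.96/√0.90 = 2.066, giving 3.9%.

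| R2 with change | SE overstated by | True type I error |
|---|---|---|
| 0 | 0% | 5.0% |
| 0.02 | 1.0% | 4.8% |
| 0.05 | 2.6% | 4.4% |
| 0.10 | 5.4% | 3.9% |
| 0.20 | 11.8% | 2.8% |
| 0.30 | 19.5% | 1.9% |

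**Step 2, simulation at the planned sizes (8,000 trials per setting).** Type I error of the unadjusted test. The first figure has effects linear in the continuous factors; the second has effects carried by the strata alone.

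| Per arm | R2 = 0 | R2 = 0.10 | R2 = 0.30 |
|---|---|---|---|
| 35 | 5.0% / 5.2% | 3.9% / 3.7% | 2.8% / 1.9% |
| 20 | 5.0% / 5.0% | 4.5% / 3.9% | 3.0% / 2.2% |
| 10 | 5.0% / 5.1% | 4.5% / 4.1% | 3.5% / 2.3% |

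The simulation standard error near 5% is √(0.05 × 0.95/8,000), about 0.24 points. With both factors in the model, type I error was 4.5% to 5.2% in every setting.

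**Step 3, power (4,000 trials per setting, linear effects).** The differences of 0.68, 0.91 and 1.33 SD are assumptions, chosen to give about 80% power unadjusted; the documents contain none of them.

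| Per arm | R2 = 0, unadjusted → adjusted | R2 = 0.10 | R2 = 0.30 |
|---|---|---|---|
| 35 | 79.3% → 78.9% | 80% → 83% | 81% → 91% |
| 20 | 79.6% → 78.8% | 80% → 83% | 82% → 91% |
| 10 | 78.3% → 76.4% | 81% → 82% | 81% → 90% |

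**Step 4, how large R2 might be.** Taking differences cancels any effect that a factor has equally on both occasions. With unit SDs and pre-post correlation ρ, a single factor correlating r_pre and r_post with the two scores has R2 with change = (r_post − r_pre)²/(2 − 2ρ). Assume ρ = 0.7, so the denominator is 0.6:

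- r_pre 0.4, r_post 0.4: R2 = 0, type I error 5.0%.
- r_pre 0.4, r_post 0.3 or 0.5: R2 = 0.01/0.6 = 0.017, about 4.8%.
- r_pre 0.4, r_post 0.2: R2 = 0.04/0.6 = 0.067, about 4.2%.

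A factor can therefore relate clearly to the score and hardly at all to its change.

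**The case against.** A reader might infer that every planned analysis ignores both factors, that the standard errors are certainly too large, and that the tests certainly run below 5%. The documents do not support this. Age is used in the predictor and moderator analyses of section 7.3. The oversized standard error arises only if age or screening score predicts change, and no document gives that relation. Eligibility also narrows the spread of screening scores: possible dementia is excluded (6.4b), the cognitively normal group must meet test cut-offs (6.4c), and the diagnostic groups are analysed separately. Values of 0.20 to 0.30 for R2 have no support in the text.

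It is also fair to say that the error is conservative and the trial is a pilot. The unadjusted difference is not biased by omitting the factors, and Cohen's d on the raw SD does not depend on the t-test's standard error. Neither document plans confidence intervals, so no planned interval is wrong. At 10 per arm and R2 = 0.10 the gain in power is about 1 point, and at R2 = 0 adjusting loses a little.

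Finally, the covariate is not ready to use. Section 7.2.a names MoCA/MMSE, while 6.4b, Table 1 and Table 2 use MoCA or the Dementia Rating Scale, and the Parkinson criteria in 6.4c cite the latter. MMSE is in neither table.

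All of this limits the size and certainty of the point. What remains is that the analysis of the main comparisons does not match the allocation, and that aligning it costs very little.

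**Conclusion.** The point holds in conditional form. The main comparisons in both documents omit the factors used to balance allocation. To the extent that those factors predict change, the tests are conservative and report less precision than the design delivers. Under an assumed two-sided 5% level, with 35 per arm, type I error is about 4.4% at R2 = 0.05, 3.9% at 0.10 and 1.9 to 2.8% at 0.30, with smaller departures at 20 and 10 per arm. At R2 of 0.02 or less the departure is about 0.2 points, which is negligible. The sizes also rest on an assumed stratified-block scheme, because the actual algorithm is not described.

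The direction is certain; whether the effect is material is not. It becomes noticeable from about R2 = 0.10. It cannot produce false positives, so it does not undermine a positive finding. It is a worthwhile improvement to the plan and does not threaten the trial's validity.

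**What to change.** Add to the SAP: within each diagnostic group, each outcome is analysed with a linear model containing treatment, age (continuous) and the cognitive screening score used for allocation. Name the instrument, or standardise the score within instrument, because the documents cite MoCA, MMSE and the Dementia Rating Scale without a common scale. Report the adjusted difference with its 95% CI alongside the unadjusted t-test and Cohen's d.

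The SAP is written in the past tense. If results were already known when the adjusted model is added, label it a supplementary analysis and leave the t-test in place.

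Cost: 2 degrees of freedom per model. At 10 per arm these fall from 18 to 16 and the critical t rises from 2.10 to 2.12. If R2 is 0, power falls by about 0.4 points at 35 per arm and about 2 points at 10 per arm. Age and a cognitive screening score are collected at screening, so no new data collection is planned for; the remaining work is to establish which instrument each participant had and to put the scores on one scale.

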6.4 Inclusion/Exclusion criteria

6.4a. General Inclusion Criteria for all Participants

- Age 62 years or above
- Able to provide informed consent and perform cognitive and mood measures on a computer
- Willingness to be randomized to Sham or Real intervention
- Can devote 2 weeks to the intervention, and additional time for pre and post testing
- 8th grade education and ability to read on 8th grade level based on scores on the Wechsler Test of Adult Reading (WTAR) or the Wide Range Achievement Test-IV (WRAT-IV); or a reading test at 14 pt. text
- On stable doses of major medications; Since some older adults with memory complaints may be prescribed acetylcholinesterase inhibitors or related medications by their primary care physicians (i.e., donepezil, rivastigmine, galantamine, memantine, or other potential memory-enhancing agent(s), we will not exclude them as long as they have been on stable medications for at least two months and plan to continue this medication during study participation.

- Willingness to allow a study partner (spouse, family member, friend) to answer questions about their cognitive, mood, and other behaviors. This does not apply to individuals with Parkinson disease.

6.4b. General Exclusion Criteria for All Participants

- Sensory loss (vision, hearing) or motor deficits that would preclude participation in the experimental cognitive tasks or neuropsychological assessment
- Unstable and uncontrolled medical conditions (metabolic encephalopathy, HIV, moderate to severe kidney or liver disease)
- Previous major strokes or other known significant brain abnormalities or diseases affecting cognition (i.e., multiple sclerosis, seizure disorder, brain surgery, moderate TBI, etc.). No history of brain surgery. Exceptions are a diagnosis of Parkinson's disease for the PD subgroup.
- Evidence of potential dementia based on cognitive screening (e.g., scores < 5th %ile on the Montreal Cognitive Assessment (MoCA) or the Dementia Rating Scale-2 (DRS-2) based on appropriate age, education and sex norms.

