6.5 Screening Interview and Measures

Participants will be screened for inclusion/exclusion criteria. This will involve review of background and demographic information, medical and psychiatric history, current medications, and assessment of functional activities, along with screening of current cognitive

status using the MoCA or DRS-2, the HVLT-R or WMS-III Logical Memory, and other cognitive measures. Screening will be administered by the project coordinator.

Table 1: Screening & Baseline Measures

Dementia Screen	Montreal Cognitive Assessment (MoCA: Nasreddine et al., 2005) or Dementia Rating Scale (DRS); these are widely used cognitive screening measures for dementia; See text for cutoff scores for Cognitively Normal and MCI groups
Objective Memory	Hopkins Verbal Learning Test-Revised and the WMS Logical Memory Stories : delayed recall scores on these measures are used to assign participants to Cognitively Normal (CN), amnestic and nonamnestic MCI groups, or to exclude Parkinson patients; (see text)
Other Cognitive measures	Executive Function - Trailmaking Test (Optional: Wisconsin Card Sort) (optional for PD) Visuospatial - Judgement of Line Orientation (JLO) (optional for PD) Language - Boston Naming Test, Category Fluency (optional for PD) Attention & Processing Speed - Digit Span, Digit Symbol (optional for PD)
Medical	Background medical history - rule out medical conditions (i.e., neurodegenerative, TBI, etc.),
	Charlson Comorbidity : Assesses for variety of comorbid medical conditions, computes risk factor score
	List of Medications : stable medications for 3 months; rule out use of anticholinergic medications; rule out use of photo-sensitive medications within 15 days of intervention
Psychiatric	Mental Health Screen V.3 (Carroll & McGinley) - this is modification of Structured Clinical Interview for DSM-IV psychiatric disorders, both current and historical (SCID-IV, First, Spitzer, Gibbon, & Williams); Goal is to rule out major depressive disorder, schizophrenia, psychosis, current substance abuse, and other Axis 1 disorders
Reading Literacy	Wechsler Test of Adult Reading (WTAR) or the reading subtest from the Wide Range Achievement Test –IV (WRAT-IV); participant reads aloud single words in order to estimate reading level; All must read on at least an 8 th grade level

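### The named stratifier, MoCA/MMSE, is missing for anyone screened only with the DRS-2, and the SAP's t-tests ignore the factors used to balance the arms

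*Protocol*

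**What the plan says.** Protocol 7.2.a assigns the cohorts separately: they "will be independently assigned to Sham and Treatment groups on a 1:1 ratio". It then says "Randomization will be stratified according to age and MoCA/MMSE scores", so that the arms do not differ in average age or cognitive status. The next sentence describes the method differently: "Treatment assignment will be pseudorandomized in order to have comparable distributions of age and cognitive screening scores across Sham and Treatment interventions". The section gives no cut-points, no way of generating the sequence, and no rule for converting one screening test to another.

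The screening sections name other instruments. Section 6.5 assesses cognition with "status using the MoCA or DRS-2, the HVLT-R or WMS-III Logical Memory, and other cognitive measures". The dementia exclusion in 6.4b, Table 1, the screen-failure text in 6.5 and the Table 2 schedule also give the MoCA or the DRS (DRS-2) as alternatives. The Parkinson criteria in 6.4c give the DRS-2 as their example of a screener.

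The SAP does not mention randomisation or stratification. Of the post-minus-baseline changes it says: "These change scores were evaluated as a function of treatment group (active, sham) using independent t-tests".

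**The concern.** A stratifier has to be a value that every participant has when allocated. As written, a participant can be screened in full accordance with the protocol, using the DRS-2, and have neither a MoCA nor an MMSE score. Someone following 7.2.a would not know which stratum to use, and a reader could not reconstruct what was done. If both screeners are used within one cohort, their raw scores are on different scales and cannot be put in order together.

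This matters because cognition is a co-primary outcome and the cohorts are small, with 10 to 35 planned per arm. A chance difference in baseline cognition can then move an estimate noticeably. The SAP intends the effect sizes to guide the choice of measures for future trials, so such a difference would carry forward.

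The second part concerns the analysis. Balancing on a prognostic factor makes the arms more alike than chance would. A t-test that leaves the factor out still counts its variation as noise, so the precision gained at allocation does not appear in the result.

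**Working it through.** **1. Instruments, place by place**

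| Place | Instrument named | MMSE? |
|---|---|---|
| 6.4b, dementia exclusion | MoCA or DRS-2 | no |
| 6.4c, Parkinson group | DRS-2, as an example | no |
| 6.5, text and Table 1 | MoCA or DRS (DRS-2) | no |
| 6.5, screen-failure text | MoCA or DRS | no |
| Table 2 and its abbreviations | MoCA or DRS-2, one row | no |
| 7.2.a | MoCA/MMSE | **yes, the only mention** |
| SAP | none | no |

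The MMSE is never scheduled, and the DRS-2 is permitted but is not named as a stratifier.

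**2. How many participants**

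Planned sizes from Protocol 6.2: 70 + 20 + 20 + 40 = 150. No text says who gets which screener, so the number with the DRS-2 only can be anything from 0 to 150. If it is the Parkinson cohort and no one else (an assumption), it is 40/150 = 27% of the sample and all of one separately randomised cohort.

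**3. What is at risk if balancing does not work**

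Under simple 1:1 allocation with n per arm, the standard error of the difference in a standardised baseline score is √(2/n). The chance of a difference beyond 0.5 SD in either direction follows from the normal distribution.

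- n = 10: √(2/10) = 0.45 SD; 0.5/0.447 = 1.12; probability about 26%.
- n = 20: √(2/20) = 0.32 SD; 0.5/0.316 = 1.58; probability about 11%.

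**4. What adjustment would gain**

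Let R² be the share of the variance of the *change score* explained by age and screening score. The documents give no such figure, so 10% and 20% are assumptions. With k = 2 covariates, cohort size N and simple randomisation, the expected variance ratio (adjusted to unadjusted) is (1 − R²) × [1 + k/(N − k − 3)]. The excess in the unadjusted standard error is 1/√ratio − 1.

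| Cohort | Cost factor | Ratio, R² = 10% | SE excess | Ratio, R² = 20% | SE excess |
|---|---|---|---|---|---|
| Each MCI group, N = 20 | 1 + 2/15 = 1.133 | 1.020 | none (adjusting loses about 1%) | 0.907 | 5% |
| Parkinson, N = 40 | 1 + 2/35 = 1.057 | 0.951 | 2.5% | 0.846 | 9% |
| Cognitively normal, N = 70 | 1 + 2/65 = 1.031 | 0.928 | 4% | 0.825 | 10% |

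Without the cost factor the excess would be 1/√0.9 − 1 = 5% and 1/√0.8 − 1 = 12%. Those figures suit a large sample. Good balance between arms reduces the cost, so a well-balanced small cohort would lie between the two sets of numbers.

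**The case against.** The best defence is the sentence that follows the stratification rule. It speaks of cognitive screening scores in general, every participant has one, and the cohorts are allocated independently. If the whole Parkinson cohort took the DRS-2, it could be balanced on the DRS-2 with no mixing of scales. That is a possible reading, and it means one cannot say that balance was unattainable. But the sentence names no instrument and differs from the sentence before it. It also does not cover a cohort in which both screeners are used, which 6.4b and 6.5 permit.

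A second defence is that this is a pilot meant to gauge effect sizes and feasibility (6.7.2), and that 7.3 already plans to examine age as a predictor of change. Both are true. Still, 7.3 does not list the screening score, and the SAP carries over neither factor.

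Some stronger inferences are tempting but not supported:

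- *That 27% is an upper bound.* It is one scenario. The DRS-2 is open to any participant, and 6.4c offers it only as an example.
- *That arms were balanced by hand and assignments were therefore predictable.* The protocol uses the term pseudorandomized and gives no mechanism. Section 6.7.4 says that devices are coded, that one investigator holds the code, and that the staff giving sessions do not know the assignment. This does not prove concealment at enrolment, but nothing shows the opposite.
- *That the design produces 16 cells with about 5 people in each MCI cell.* This needs two levels per factor (4 cohorts × 2 × 2 = 16; 20/4 = 5), and no levels are stated.
- *That the SAP loses 5% to 12% in every cohort.* This omits the cost of estimating the covariates, which matters at N = 20.

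**Conclusion.** The inconsistency is real. Section 7.2.a relies on a test that is never scheduled and omits one that the screening sections permit. The named stratifier is therefore missing for everyone screened with the DRS-2 alone, a number the documents leave open. The allocation cannot be reproduced from the text.

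The loss of precision in the SAP analysis is conditional: age and screening score must predict change, and the R² values are assumptions. It is modest in the cognitively normal cohort and may vanish in the MCI cohorts.

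A reader might conclude that the comparison of arms is biased. The documents do not support that: an unclear stratifier weakens the assurance of balance, and an unadjusted t-test of randomised arms is not biased for leaving it out. The point is worth correcting but does not invalidate the trial.

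**What to change.** **Protocol.** Reconcile 6.4b, 6.4c, 6.5, Tables 1 and 2, and 7.2.a. Delete the MMSE and name as stratifier the screener actually used in each cohort, with its cut-points. If both screeners are used within a cohort, use the norm-referenced percentile, since 6.4b already applies norms to both. Two drawbacks should be stated: percentiles from two tests are only approximately comparable, and percentiles normed for age, education and sex do not balance raw scores.

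**Allocation.** If it is still open, specify a computer-generated scheme with a random element, run within cohort. The SAP is written in the past tense, so allocation may be complete. In that case report the method and stratifier actually used, and tabulate baseline age and screening score by arm within each cohort.

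**SAP.** Analyse change with a linear model containing treatment arm, age and the screening score used for balancing. Section 7.3 analyses the cohorts separately and the SAP is silent on this, so add a cohort term only if cohorts are pooled. The gain is clearest in the cognitively normal cohort or a pooled analysis. In the two MCI cohorts, keep the unadjusted result alongside.

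**Cost.** A few sentences in each document, no new test, and two degrees of freedom per cohort analysis. If allocation has closed, the reporting and the adjusted analysis are all that can still be changed.

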6.2 Participants

Participants will include individuals, age 62 years and older, who are independently living and willing to undergo a two-week intervention program. Our study groups will consist of the following: 70 cognitively normal individuals (N= 35/group), 20 individuals with amnestic MCI (N=10/group), 20 individuals with nonamnestic MCI (N=10/group), and 40 nondemented individuals with Parkinson disease (N=20/group). Based on our previous intervention studies with older adults, we anticipate a 20% attrition rate and up to 50 screen failures. To account for screening failures and study attrition, we anticipate consenting 206 individuals.

Informed Consent: Informed consent will be obtained according to university and federal guidelines. The informed consent process may begin with the initial telephone screening call, when a prospective participant is contacted or calls to find out more information about the study (See Telephone Script). After that first phone contact, the participant will be sent a copy of the Informed Consent via hardmail or via email if they are interested, and/or scheduled for an appointment in the VITAL laboratory or at the Fixel Center for Neurologic Diseases to discuss the study in more detail and in person.

Other potential participants, particularly those seen during the clinics of the PI or co-investigators, will be directly asked about their interest in this study and will be provided a copy of the informed consent to review.

During the first study visit, the project will be explained in more detail to the potential participant by the study coordinator or approved staff and the Informed Consent will be reviewed. Participants will be informed that this is a randomized trial and that there is 50% likelihood they may receive the sham intervention. The participant will be given the opportunity to ask questions. No study interventions will begin until the Informed Consent

(ICF) paperwork is signed. Participant will be given a signed copy of the ICF paperwork, and a copy will be kept on file with the Principal Investigator.

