6.6.5 Other Measures

6.6.5a. Placebo Control Questionnaire (PCQ): This is a 4-item questionnaire that is given after the end of the 2-week intervention. It asks questions regarding which group (real, sham) the participant believes they were assigned.

6.6.5b. Adverse Events Log (AE). This is a standard open ended questionnaire regarding symptoms or adverse events that the participant has experienced since beginning the intervention. This will be assessed at the end of each intervention session and will prompt for symptoms the participant may have experienced during the session and/or since the previous intervention session. It queries for severity, how long the symptoms last, and whether (if known) the symptom might be related to the intervention. This will also be assessed during the followup session.

6.6.5c. Fitzpatrick Skin-Type Questionnaire (Fitzpatrick, 1986): This is a 10 item self-report form where participants indicate hair, eye, and skin color, as well as rate burning and tanning to sun exposure. This information is being obtained because skin and hair pigmentation may impact the penetrance of infrared light through the skin and scalp. This scale is often used in dermatology and will be used to as a covariate in statistical analyses.

6.6.5d. Cognitive Change Index (CCI) On this 20 item questionnaire, participants rate changes in their own thinking and memory. They use a 5 point Likert scale that goes from 1 (no problem/normal ability) to 5 (much worse/severe problem). Domains that are covered include multi-tasking, learning new things, recalling old memories, thinking quickly, retrieving names, etc. This questionnaire will be given before and after the intervention to assess perceived changes.

6.6.5e. Expectancy Questionnaire: This measure is given prior to the intervention and asks participants to rate their expectations about changes they anticipate will change as a result of the intervention.

6.6.5f. Followup Questionnaire: This measure is given after the intervention. It asks participants to rate the extent that they experienced changes in particular cognitive and functional domains

6.6.5g. Pittsburgh Sleep Quality Index: This is well-known and well-validated sleep scale for detecting insomnia and sleep quality. It will be given before and after the intervention.

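### After a participant stops treatment, adverse-event enquiry depends on a voluntary return visit, and no adverse-event summary by arm is planned

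*Protocol*

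**What the plan says.** **Collection.** Protocol section 6.6.5b says of the adverse-event log: "This will be assessed at the end of each intervention session". Each enquiry covers that session and the time since the previous one, and the log is repeated at the follow-up session. Table 2 marks the log in the intervention and follow-up columns only. Sections 6.7.3, 9 and 10 follow the same visits, and section 12 ties side-effect questions to visits.

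**People who stop.** Section 7.2.b says "participants who are unwilling/unable to continue with intervention will be encouraged to attend the post intervention testing, if possible". No telephone call, early-termination contact or record of the reason for stopping is described. Section 6.2 states "we anticipate a 20% attrition rate and up to 50 screen failures".

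**Review and reporting.** Section 10 provides for study staff to go through the questionnaires with each participant, for IRB reporting of events of sufficient concern, and for a monthly email to the team on the nature of events. None of this is split by arm.

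**Analysis.** Section 7.1 lists no safety outcome. Section 7.3 covers cognition, mood, imaging and motor measures. The SAP says "we examined cognitive and emotion outcome variables using change scores" and does not mention adverse events.

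**The concern.** Stopping treatment can itself be a sign of poor tolerability. Under this schedule, someone who feels unwell at home after a session, or during an optional home intranasal session, and then stops is asked about it only by coming back. The return visit repeats a test battery of about 3 to 3.5 hours, which is a high price for one safety enquiry. The home usage log and journal are described as recording device use and treatment times, not symptoms.

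Within an arm, missed events can only lower the recorded count. The effect on the difference between arms depends on whether stopping and non-return differ between active and sham.

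The second gap concerns the data that are collected. The protocol hopes to lead to trials of dosage parameters (section 3 summary) and notes in section 8 that only two earlier human studies were sham-controlled. A blinded comparison of tolerability against sham is something this design can supply, but the plan does not call for it.

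**Working it through.** **1. What the log covers.** A completer has 6 session enquiries + 1 follow-up enquiry = 7. Because each one looks back to the previous session, a completer is covered from first session to post-test. Someone who attends k sessions and does not return has k enquiries, and nothing is scheduled after session k. With k = 3, that is 3 of 7.

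**2. The plan's own figure.** No adverse-event rate or return rate is stated. The only figure tied to dropout is in section 6.2: "we anticipate consenting 206 individuals". Planned sample: 70 + 20 + 20 + 40 = 150, allocated 1:1, so 75 per arm. Adding 50 screen failures:
- 150 / (1 − 0.20) = 187.5, rounded up to 188; 188 + 50 = 238
- 150 × 1.20 = 180; 180 + 50 = 230
- 150 + 50 = 200, with no attrition allowance

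None gives 206. Working back, 206 − 50 = 156. This mismatch is a separate matter, but it leaves the number randomised unsettled, so three values are used below.

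**3. People without an enquiry after their last session.** For R randomised and a return rate r among dropouts (assumed, full range shown), the number is 0.20 × R × (1 − r).

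| R | Dropouts | r = 0% | 25% | 50% | 75% | 100% |
|---|---|---|---|---|---|---|
| 150 | 30 | 30 | 22.5 | 15 | 7.5 | 0 |
| 156 | 31.2 | 31.2 | 23.4 | 15.6 | 7.8 | 0 |
| 188 | 37.6 | 37.6 | 28.2 | 18.8 | 9.4 | 0 |

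These are upper figures, because they treat every dropout as a treatment stop. They count people with no later enquiry, not people with a missed event.

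**4. Which analysis set would hold the events.** The set called intention-to-treat needs at least 1 week of intervention. The second set needs at least 80% of the assigned treatment, and 0.80 × 6 = 4.8 laboratory sessions. Someone who stops in the first week is in neither, so a safety table built on either set would leave out the earliest stoppers.

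**5. What a zero count would mean.** The exact two-sided 95% upper limit for 0 events in n is 1 − 0.025^(1/n).

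| n per arm | Group | Upper limit |
|---|---|---|
| 75 | All groups together | 4.8% |
| 35 | Cognitively normal | 10.0% |
| 20 | Parkinson disease | 16.8% |
| 10 | Each MCI group | 30.8% |

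**6. Why the table should be descriptive.** With assumed event rates of 15% active and 5% sham and a two-sided 0.05 test, power is 53% at 75 per arm, 28% at 35, 18% at 20 and 11% at 10. Counts with intervals are informative at these sizes; a significance test is not.

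**The case against.** Much of the safety process is in place. The log is completed after every attended session, including the last, and looks back over the interval before it. Stoppers who return complete it again. Staff review the questionnaires with each participant, and events of sufficient concern go to the IRB. Encouraging someone to return implies some contact, during which a reason may well be asked. No aim concerns safety, and the protocol describes the device as non-significant risk. The SAP is in the past tense, so new calls may no longer be possible.

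Most of this stands and limits the point. A reader might infer four stronger things that the documents do not support:

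- **That the events most likely to reveal harm are lost.** Events up to the last attended session are collected. The exposed part is what starts or worsens afterwards in people who do not return.
- **That event data go only into an email.** Section 10 also provides participant-level review and IRB reporting.
- **That some definite number, such as half the dropouts, will be missed.** No return rate is given.
- **That the trial plans to conclude there are no side effects.** The wording to that effect in section 6.7.2 describes prior investigations.

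The zero-event limits in step 5 reflect sample size and would apply with complete follow-up too. They show how to report a low count and do not measure the loss.

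The objection does not supply a specified enquiry for stoppers who stay away, or a by-arm summary.

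**Conclusion.** The concern holds in two limited parts. First, adverse-event ascertainment after stopping rests on a visit that is only encouraged, so late events in non-returners can go unrecorded, possibly including the reason for stopping. Second, no adverse-event summary by arm is planned in the protocol or the SAP.

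On 150 randomised, between 0 and 30 people (0 to 20%) could lack any enquiry after their last session. This rests on the stated 20% attrition, on an unknown return rate, and on counting every dropout as a treatment stop. The SAP refers to a small N, so the achieved numbers may be lower than planned and the exact limits wider. The gap leaves the efficacy comparison untouched. It is an inexpensive improvement to safety reporting.

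**What to change.** **Protocol sections 7.2.b and 10.** For anyone who stops, complete the existing adverse-event log by telephone shortly after stopping and again when the post-test would have been due. Record the reason for stopping whether or not the person attends. State that this also covers Parkinson participants withdrawn at the post-intervention off-medication visit (section 6.6), for whom no adverse-event contact is specified.

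**SAP.** Add one descriptive table by arm, overall and within each participant group, in everyone who received at least one session. Show the number of participants with any event, with any possibly related event, and who stopped because of an event, each with an exact 95% interval. Report the upper limit beside any zero count.

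**If follow-up is complete.** Build the by-arm table from the existing logs, and state that events after stopping in people who did not return were not ascertained.

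**Cost.** At most two short calls each for about 30 people, or 60 calls, using a form already in use, plus one table. The downside is a little staff time and a less favourable safety statement.
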